8.2 Efficacy Assessments and Procedures

Not Applicable.

8.3 Safety Assessments and Procedures

The safety of CHS-1420 and HUMIRA® will be assessed by AEs, SAEs, vital signs, physical examination, laboratory test results, ECG, local reactions at the injection site, concomitant therapy, *etc.*

8.3.1 Physical Examination

Physical examination will be performed at the screening visit, and before discharge from the trial on Day 65. A full physical examination includes assessment of skin, mucous membranes, lymph nodes, head, neck, chest, abdomen, spine/limbs and nervous system, *etc.* And also, a symptom-based physical examination will be performed on Day 4 before leaving the site.

Injection site assessment will be performed during screening, within 1 h pre-dose and at 1 h (± 30 min), 4 h (± 60 min), 12 h (± 60 min), 24 h (± 60 min), 48 h (± 60 min) post-dose.

8.3.2 Vital Signs

Vital signs (including systolic and diastolic blood pressure, pulse rate and temperature) will be measured at screening, within 1 h pre-dose and at 1 h (± 30 min), 2 h (± 30 min), 8 h (± 60 min), 12 h (± 60 min), 24 h (± 60 min), 48 h (± 60 min), 72 h (± 60 min) post-dose, as well as on each OPV day (the same requirement of timewindow for vital signs measurement on OPV days as that for PK sampling).

Normal reference ranges (inclusive) for vital signs are listed as follows:

- Temperature (forehead): 35.8 to 37.5°C
- Pulse rate: 50 to 100 beats per minute
- Systolic blood pressure: 90 to 140 mmHg
- Diastolic blood pressure: 60 to 90 mmHg

8.3.3 Electrocardiograms

The 12-lead ECGs will be tested at the screening visit, and before discharge from the trial on Day 65.

8.3.4 Clinical Laboratory Assessments

The clinical laboratory tests, including biochemistry, hematology, urinalysis, coagulation function, serum pregnancy test (only for females), will be performed at the screening visit (the results obtained within 7 days considered acceptable), and on Day 4, Day 16, Day 30, Day 65. In addition, serum pregnancy results for females will also be confirmed before admission on Day -1. A list of clinical laboratory assessments is included in Section 13.2.

8.4 Adverse Events and Serious Adverse Events

8.4.1 Definitions of AE and SAE

Adverse Event (AE) – Any untoward medical occurrence in a clinical investigation participant administered a pharmaceutical product and that does not necessarily have a causal relationship with this treatment. An AE can therefore be any unfavorable and unintended sign (including an abnormal laboratory finding), symptom, or disease temporally associated with the use of a medicinal (investigational) product, whether or not related to the medicinal (investigational) product.

Serious Adverse Event (SAE) – Any untoward medical occurrence that at any dose:

- Results in death,
- Is life-threatening,
- Requires inpatient hospitalization or prolongation of existing hospitalization,
- Results in persistent or significant disability/incapacity, or
- Is a congenital anomaly/birth defect.

Suspected Unexpected Serious Adverse Reaction (SUSAR) – an adverse reaction that meets three criteria: suspected, unexpected and serious.

- Suspected: There is a reasonable possibility that the drug caused the adverse drug reaction.
- Unexpected: An adverse reaction, the nature or severity of which is not consistent with the applicable product information (e.g., the reference safety information).
- Serious: See above for SAE.

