2.2 Summary of Benefits and Risks

Benefits

This is a single-center, randomized, single-blind, single-dose, parallel-group trial to assess

the pharmacokinetic similarity between CHS-1420 40 mg/0.4 mL and HUMIRA® (Adalimumab) 40 mg/0.4 mL in healthy Chinese adult participants under fasting conditions. No benefits are expected for the individual participant. However, the trial data may support the registration application for a proposed biosimilar to HUMIRA® (Adalimumab), which can further provide an alternative therapeutic choice and benefit the indicated population.

Risks

CHS-1420 40 mg/0.4 mL, developed by Hong Kong King-Friend, a subsidiary corporation of Nanjing King-Friend Biochemical Pharmaceutical Co., Ltd., is designed as a biosimilar to HUMIRA® (Adalimumab). Data derived from analytical studies, animal studies indicated similarity between CHS-1420 and HUMIRA®.

For individual participant, the risks of treatment with HUMIRA® (Adalimumab) can be found in the Prescribing Information [2]:

Most common adverse reactions (>10%) during HUMIRA® (Adalimumab) treatment are: infections (e.g. upper respiratory, sinusitis), injection site reactions, headache and rash.

Other warnings and precautions for treatment with HUMIRA® (Adalimumab) are as follows:

- *Serious infections:* Do not start Adalimumab during an active infection. If an infection develops, monitor carefully, and stop Adalimumab if infection becomes serious.
- *Invasive fungal infections:* For patients who develop a systemic illness on Adalimumab, consider empiric antifungal therapy for those who reside or travel to regions where mycoses are endemic.
- *Malignancies:* Incidence of malignancies was greater in Adalimumab-treated patients than in controls.
- *Anaphylaxis or serious hypersensitivity reactions:* may occur.
- *Hepatitis B virus reactivation:* Monitor HBV carriers during and several months after therapy. If reactivation occurs, stop Adalimumab and begin anti-viral therapy.
- *Demyelinating disease:* Exacerbation or new onset, may occur.
- *Cytopenias, pancytopenia:* Advise patients to seek immediate medical attention if symptoms develop, and consider stopping Adalimumab.
- *Heart failure:* Worsening or new onset, may occur.
- *Lupus-like syndrome:* Stop Adalimumab if syndrome develops.

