In one PK similarity study^[3] on the proposed biosimilar to Adalimumab, following a single subcutaneous injection at dose of 40 mg in healthy participants, approximately 70% participants reported at least one adverse event of which the majority were mild or moderate in intensity. The most commonly reported TEAEs, independent of relation to

study treatment, were headache, nasopharyngitis, and rhinitis. Other adverse events included Upper respiratory tract infection, Back pain, Myalgia, Oropharyngeal pain, Fatigue, Neutropenia. There were two SAEs: an angioedema (moderate intensity), which was considered to be related to the study treatment (the proposed biosimilar product arm), and a femoral neck fracture (severe intensity), which was not considered to be related to the study treatment (US- HUMIRA arm).

For the whole clinical trial, participants will suffer venous sampling at the scheduled frequency which may lead to local reactions, e.g. swelling and stiffness, etc. In addition, there may be occurrence of blood pressure fluctuations, dizziness, nausea, even fainting, etc. upon the blood collection in clinical practice.

During the screening period, participants will be fully informed of the trial purpose, investigational product information, dosing regimen (such as dosage, administration method, period, etc.), clinical observation, frequency and procedure of blood collection, potential risks, compensation and indemnity to ensure the voluntary participation and the participant compliance. At the same time, investigators should learn participants' previous reactions and tolerance to venous blood collection to avoid enrollment of participants not tolerable with the venous sampling in the trial.

During the clinical trial, the investigator should pay close attention to the previous reported SAEs, common AEs and AEs leading to discontinuation, and make participants fully informed and establish the relevant plan of monitoring and treatment. After the treatment in each period, clinical staff should closely observe the participants for possible AEs and related symptoms.

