8.5 Pregnancy and Postpartum Information

Any pregnancy during the trial which occurs in a female participant or the partner of a male participant must be reported to the Ethics Committee by investigators within 24 h after being informed. The pregnant female participant must withdraw from the trial, and the pregnancy should be recorded, reported to the applicable agencies and followed up. When a pregnancy occurs in the partner of a male participant, the male is not required to withdraw, however, the pregnancy should be recorded, reported and followed up in the same way as the management for the pregnancy of the female participant. Results of the pregnancy should be recorded and reported. The pregnancy must be traced until at least 8 weeks after the end of pregnancy.

The pregnancy will not be treated as an AE. The pregnancy of which the outcome meets criteria for SAEs (such as spontaneous abortion, stillbirth, neonatal death, congenital malformations, ectopic pregnancy or pre-eclampsia) should be reported as SAEs. Any SAE will be reported through the SAE reporting process.

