12.2 Further Details and Clarifications on the SAE Definition

Hospitalization is warranted or prolonged which will not be treated as SAEs in the following conditions:

- For diagnosis or elective surgery for the existing diseases;

- For efficacy assessment in the trial;
- For predefined course of treatment for the studied disease in the trial;
- For medical reimbursement consideration;
- Scheduled hospitalization outlined in the protocol;
- Hospitalization planned prior to the trial;
- For elective surgery not for an AE;
- For comprehensive medical examination.

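### The SAE definition is a closed list of five criteria with no important-medical-event criterion, so some medically important reactions treated on site or as an out-patient would be missed as SAEs

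*Protocol*

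**What the plan says.** Protocol 8.4.1 lists five outcomes that make an event serious. The third is "Requires inpatient hospitalization or prolongation of existing hospitalization". The fourth reads "Results in persistent or significant disability/incapacity, or" and the fifth, "Is a congenital anomaly/birth defect", ends the list. SAP 5.6.1 repeats the same five. For a SUSAR, 8.4.1 takes seriousness by cross-reference: "Serious: See above for SAE".

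Protocol 12.2, which clarifies the SAE definition, only takes events out. One of its exemptions is "Scheduled hospitalization outlined in the protocol". The synopsis confines every participant from one day before dosing until 72 hours after it, and the schedule of activities labels those days as hospitalization.

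Protocol 8.5 does not count pregnancy itself as an adverse event. It does require SAE reporting where the outcome meets SAE criteria, and gives examples: "such as spontaneous abortion, stillbirth, neonatal death, congenital malformations, ectopic pregnancy or pre-eclampsia".

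Three provisions use the definition. Section 8.4.6 sets the written report to the sponsor, usually within 24 hours, and also says that a participant with an SAE is to be discontinued. Section 8.4.8 sets expedited reporting of SUSARs. Section 9.5 has SAEs summarized for the safety comparison.

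**The concern.** Seriousness and severity are different things. An event can be of moderate grade and still need prompt attention from the sponsor because treatment prevented something worse. With a closed list of outcomes, the investigator has no way to call such an event serious on judgement.

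This design makes the gap wider than it would be in an out-patient trial. An event severe enough to send a participant to hospital would normally qualify through admission. Here the participant is already in the facility during the first 72 hours, so an admission cannot mark the event out. Only a longer stay would clearly do so.

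At stake are the speed with which the sponsor hears of such an event and the completeness of the SAE count. Safety is a secondary objective of the trial.

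**Working it through.** No arithmetic bears on the definition, and the plan states no figure for it. The check sets the provisions side by side.

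**1. Is the list closed?** In 8.4.1 the conjunction stands at the end of the fourth item, and only one item follows. No open-ended wording comes before or after. SAP 5.6.1 is the same. Wording about medical significance appears only in the Grade 3 severity description (Protocol 12.3, SAP 5.6.1), and nothing links that grade to seriousness.

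**2. A reaction during the stay.** Take a reaction on Day 1 that needs treatment on site and resolves before the planned release at 72 hours.

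- Death: no.
- Life-threatening: no, by assumption. If yes, it is captured.
- Hospitalization or prolongation: the stay was scheduled and is exempt under 12.2, and it is not extended. If it is extended, the event is captured.
- Disability: no.
- Congenital anomaly: no.

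None of the five is met. The event is an AE but not an SAE, and by cross-reference it cannot be a SUSAR.

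**3. An event after release.** Haematology and biochemistry are tested on Days 16, 30 and 65. A marked laboratory abnormality or new symptom that the investigator considers medically important, but manages without admission, runs through the same list with the same result. The gap is therefore not confined to the stay, which covers 72 of the 1,536 hours of post-dose follow-up (72/1,536 = 4.7%). That is a share of time, not of risk.

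**4. What such an event keeps and loses.** It is still recorded with its severity (8.4.4), followed to resolution or stabilization (8.4.5), graded (12.3) and tabulated (9.5). It does not start the 24-hour report in 8.4.6 and is not in the SAE count. If it is suspected and unexpected, it also misses SUSAR assessment under 8.4.8.

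**5. The examples in 8.5 against the five criteria.**

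- Stillbirth and neonatal death can fit death.
- Congenital malformations fit the congenital-anomaly criterion.
- Ectopic pregnancy and pre-eclampsia can fit threat to life or hospitalization.
- Spontaneous abortion managed without admission fits none clearly, unless fetal loss is read as death.

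So one example in 8.5 does not sit cleanly under 8.4.1, and the two sections need reconciling.

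**The case against.** The best case for the plan has four parts.

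*The wording may already reach the ward case.* Section 8.4.1 asks whether the event requires inpatient care, not whether it adds an admission, and 12.2 may exempt only the planned stay itself. This is a possible reading, so the text is ambiguous rather than inoperative. But a site could equally read it the other way, and this reading does nothing for out-patient events.

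*Safety data are not lost.* This stands. All AEs are collected and graded, and the termination criteria in 10.5.1 work on grade, not SAE status. One definition applies to both arms and the assessing investigators are blinded, so no bias towards either product is shown.

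*SUSAR reporting and unblinding are largely untouched for the obvious examples.* A reader might infer that a hypersensitivity reaction, demyelination or cytopenia would escape expedited reporting because of the gap. The documents do not support that. Section 2.2 takes these risks from the prescribing information, and a SUSAR must also be unexpected in nature or severity. Most such events would not be SUSARs under any SAE definition. For them the loss is the 24-hour report and the SAE count.

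*Other routes may exist.* A reader might conclude that no second rapid route is available, since 8.4.9 defines no events of special interest. That cannot be asserted. Section 8.4.7 is not in the text available for review. Section 8.4.8 has the sponsor evaluate safety information whatever its source, under external reporting documents whose definitions are not reproduced. What can be said is that sites will classify events from 8.4.1.

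**Conclusion.** The point holds in a limited form. Both documents lack an important-medical-event criterion. Because of the scheduled stay and its exemption, a non-life-threatening, non-disabling reaction that does not prolong the stay falls outside the SAE definition on a plain reading. So does a medically important event managed without admission. The consequence is a missed 24-hour report and an understated SAE count, plus missed SUSAR assessment where the event is also suspected and unexpected.

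No number can be put on it. It is tempting to take a size from the cited study in 2.2, where one of two SAEs was "an angioedema (moderate intensity), which was considered to be related to the study treatment". That passage does not say which criterion made the event serious, when it occurred or whether the participant was admitted. It cannot show that this protocol would have missed it, and another trial's count is not an estimate for this one.

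A reader might also infer that 8.5 depends on the absent criterion. It does not say so. It is conditional on SAE criteria being met, most of its examples can fit the five, and it names spontaneous abortion as reportable anyway. What remains is one example to reconcile.

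The conclusion rests on the plain reading of 8.4.1 and 12.2, and on the unseen section 8.4.7 and the external reporting documents not changing how sites classify events. Sample size, alpha, power and the planned primary analysis are not affected.

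**What to change.** Add a sixth criterion to Protocol 8.4.1 and SAP 5.6.1: an important medical event that, in the investigator's judgement, may jeopardize the participant or need intervention to prevent one of the listed outcomes. State in 12.2 that the scheduled stay does not exempt an event that would otherwise have led to admission. Then check the examples in 8.5 against the revised list so that the sections agree.

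The drafting cost is a few sentences and one eCRF option, with possibly a few more SAE reports.

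There is one knock-on effect to settle at the same time. Section 8.4.6 ties SAE status to discontinuation, and 7.1 does not allow withdrawn participants to continue. In a single-dose trial with sampling to Day 65, a wider SAE definition could on that wording end a participant's later PK sampling and cost the AUC0-∞ value. The sponsor must reconcile those passages with the wider definition so that its effect on follow-up sampling is clear.

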8.4.2 Time Period and Frequency for Collecting AE and SAE Information

The nursing and medical staff will closely observe the participants for any AEs throughout the trial. Once dosed, any abnormalities of clinical significance e.g. clinical sign and symptom, vital signs, physical examination, ECG, laboratory test results in a participant will be collected as AEs or SAEs until completion of the trial.

Before leaving the research facility, the participants will be informed by the staff of the precautions and to report any AEs until completion of the trial.

8.4.3 Identifying AEs and SAEs

Adverse events will be monitored by nursing and medical observations of the staff and spontaneous reporting throughout the trial. The inquiry to participants for AEs from Investigators should be performed in an non-induced manner during the trial.

8.4.4 Recording of AEs and SAEs

During the trial, the AEs record form should be truthfully filled, including the time of onset, duration, severity, action taken and follow-up outcome. The AEs should be documented on the designated CRF.

Abnormal laboratory test results of no clinical significance will not be recorded as AEs or SAEs. Laboratory abnormalities (e.g. biochemistry, hematology, urinalysis, and coagulation function) and other abnormality (e.g. ECG, vital signs) of clinical significance must be recorded as AEs or SAEs. If the abnormal results are the part of a syndrome, the syndrome or diagnosis results (e.g. anemia) need to be recorded rather than laboratory test results (e.g. hemoglobin decrease).

Further details on assessing severity and causality of AEs and SAEs are in [Appendix 12.3](#) and [Appendix 12.4](#).

8.4.5 Follow-up of AEs and SAEs

All the AEs, whether related to the medicinal (investigational) product or not, should be followed up until the symptoms recuperate, laboratory test values return to normal or baseline level, the abnormality is irreversible or otherwise can be explained appropriately, or the participant is lost to follow up. For clinically significant abnormalities, if warranted, can be confirmed by retests. In brief the AEs during the trial should be followed up until AE resolution or stabilization, or participants lost to follow up.

8.4.6 Reporting of SAEs

When SAE occurs, the participant should be discontinued and the appropriate treatment should be provided. The investigator should inform the sponsor or the designee immediately (usually within 24 hours after awareness of the SAE) in a written form followed by detailed follow-up reports. The first report should include the following information as complete as possible: sources of the report; basic information of the participant; the investigational drug name; name, duration, severity, relationship with the investigational drug and outcomes of SAE, and any action taken. Either the first or the follow-up reports should present the participant with the clinical identification code rather than the real name, identity card number, and address.

For SAEs involving deaths, the investigator should provide the sponsor and the ethics committee with other required information, such as autopsy reports and final medical reports.

8.4.8 Serious and Unexpected Adverse Reaction Reporting

Once receives safety information in spite of the source, the sponsor should immediately analyze and evaluate the severity, correlation with the investigational products, and whether it is an expected event, *etc*. If judged to be suspected unexpected serious adverse reaction, reports should be expedited and submitted to the investigators, the clinical facility, the ethics committee, the authorities e.g. NMPA or medical institutions according to the Expedited Report Standards and Procedures for Safety Data during Drug Clinical Trial issued by China CDE in April 2018. The expedited report is also recommended when consensus may not be able to be reached on the causality between AEs and the investigational drug by Sponsor and investigators and the relatedness to the investigational drug may not be excluded by either sponsor or investigators. And sponsor will perform safety reporting to FDA according to Sponsor Responsibilities — Safety Reporting Requirements and Safety Assessment for IND and Bioavailability/Bioequivalence Studies issued by FDA in June 2021.

8.4.9 Adverse Events of Special Interest

Not applicable.

8.4.10 Disease-related Events or Outcomes Not Qualifying as AEs or SAEs

Not applicable since healthy participants will be enrolled in the trial.

8.5 Pregnancy and Postpartum Information

Any pregnancy during the trial which occurs in a female participant or the partner of a male participant must be reported to the Ethics Committee by investigators within 24 h after being informed. The pregnant female participant must withdraw from the trial, and the pregnancy should be recorded, reported to the applicable agencies and followed up. When a pregnancy occurs in the partner of a male participant, the male is not required to withdraw, however, the pregnancy should be recorded, reported and followed up in the same way as the management for the pregnancy of the female participant. Results of the pregnancy should be recorded and reported. The pregnancy must be traced until at least 8 weeks after the end of pregnancy.

The pregnancy will not be treated as an AE. The pregnancy of which the outcome meets criteria for SAEs (such as spontaneous abortion, stillbirth, neonatal death, congenital malformations, ectopic pregnancy or pre-eclampsia) should be reported as SAEs. Any SAE will be reported through the SAE reporting process.

